UCL	University College London
UHW	University Hospital Wales

3 Study Synopsis

Title	Measuring Physical Activity Levels in Critical Care: A Feasibility Study (ACTIVE)
Sponsor name	University College London Institute of Child Health
IRAS ID number	238464
Primary objective	To establish the feasibility of using a wearable accelerometer to measure the activity levels of patients recovering from critical illness
Secondary objective (s)	To quantify the activity levels of critical care patients on a single critical care unit
Study Design	Prospective observational study
Study Endpoints	Date of last participant's discharge from critical care
Sample Size	Target sample size: 15
Summary of eligibility criteria	Patients admitted to critical care at University Hospital Wales, Cardiff will be eligible for the study if they meet the inclusion criteria: 
 • Age >18; • 'At risk' of physical morbidity as determined by NICE CG83 guidelines (Appendix C); • Consent or advice obtained
Intervention	Participants will wear an accelerometer device attached to their thigh and any observed activity will be recorded. There is no direct intervention.
Procedures: Screening & enrolment	All new patients admitted to the critical care unit will be screened for eligibility. Consultee advice will initially be sought before participant re-consenting when appropriate.
Baseline	Baseline demographic information recorded
Treatment period	A wearable accelerometer device will be worn for the duration of the participant's critical care admission. Any observed activity will also be recorded
End of Study	13 th August 2018

Contents Table

1	Amendment History	2
2	Abbreviations	3
3	Study Synopsis	4
4	Introduction	7
4.1	Background and Rationale	7
5	Objective and purpose	8
6	Study Design	8
6.1	Description of study design	8
7	Population	8
7.1	Inclusion Criteria	9
7.2	Exclusion Criteria	9
8	Study Procedures	9
8.1	Recruitment	9
8.2	Informed Consent	10
8.3	Screening and Eligibility Assessment	10
8.4	Baseline Assessments	11
8.5	Data Collection	11
8.6	Subsequent Visits	12
8.7	Study Duration	13
8.8	Discontinuation/Withdrawal of Participants from Study	13
8.9	Definition of End of Study	13
9	Statistics	13
9.1	Statistical methods / plan of analysis	13
10	Data Management	14
10.1	Source Documents	14
10.2	Direct Access to source data / documents	14
10.3	Data Recording and Record Keeping	14

4.1 Background and Rationale

Patients admitted to critical care have a variety of life threatening conditions which require specialist care, often including a period of sedation and mechanical ventilation. As a consequence of critical illness, survivors often experience multiple sequela, including muscle weakness which leads to reduced mobility and physical function, persisting beyond discharge back into the community (Griffiths and Hall., 2010).

Guidelines for rehabilitation after critical illness (NICE CG83, 2009), enable identification of patients at risk of developing physical morbidity and provide recommendations to support the rehabilitation of these patients. Rehabilitation has been demonstrated to be safe and feasible within critical care, with traditional barriers to intervention gradually reducing (Nydahl et al., 2017). Many studies have examined rehabilitation of critically ill patients using a variety of measures, which demonstrated positive physiological and functional outcomes at various end-points, with evidence supporting early intervention (Kayambu et al., 2013). Despite this, recent studies suggest there may be disparity between the evidence supporting rehabilitation and the reality of clinical practice, with very low levels of overall physical activity demonstrated in this population (Connolly et al., 2017; Berney et al., 2015). There could be several reasons for this, but it does suggest that measurement of activity levels beyond specific exercise rehabilitation input provides a more realistic picture of a patient's physical recovery. Therefore, activity levels may be a more useful measurement of recovery than the amount of physical rehabilitation intervention or specific functional measurements.

Currently only one study in the UK (Connolly et al., 2017) has measured patient activity during critical care admission, using behavioural mapping. Although this method can provide detailed information, it does not measure patient activity continuously and is time consuming to perform. An alternative method of measuring physical activity in this population is using wearable technology, which allows continuous measurement of activity, with minimal time and resource requirements. It provides researchers and clinical staff with detailed information and, as exercise based interventions become more prevalent in critical care, research suggests wearable technology is likely to be increasingly useful to monitor progress (Verceles and Hager, 2015).

Many types of wearable device exist but few have been used in critical care. One study examined activity levels of patients within an Australian critical care unit (Beach et al., 2017) using a motion sensor armband. Although deemed to be a feasible physical activity monitor in this patient group, the motion sensor was unable to capture changes in patient position which, for this low activity population, may be an important factor. An accelerometer, which can detect changes in position, may be a more appropriate method of monitoring activity on critical care (Beach et al., 2017). Therefore, this study will aim to evaluate the feasibility of using a wearable accelerometer device to measure physical activity in patients recovering from critical illness. Those patients at higher risk of physical morbidity based on NICE guidelines (2009) will be recruited as this will allow evaluation of the device in those most likely to be minimally active and whose length of admission is more likely to be long enough to establish the feasibility of using the device within critical care.

5 Objective and purpose

Objectives	Outcome Measures/Endpoints
Primary Objective To establish the feasibility of using a wearable accelerometer to measure the activity levels of patients recovering from critical illness	Feasibility outcomes will be assessed: Wear time (hours per day) Number of days worn Number of adverse events Percentage of activities observed by nursing staff recorded by activPAL™ device. (Reasons for removal of device will be recorded if applicable)
Secondary Objectives To quantify the activity levels of critical care patients on a single critical care unit	Amount of time spent performing activity Amount of time spent sitting in chair Amount of time spent in bed

6 Study Design

6.1 Description of study design

The study will be a single-centre, prospective observational study involving patients admitted to the critical care unit at University Hospital of Wales (UHW).

The study is a feasibility study to evaluate the use of this wearable device within critical care. A priori criteria for feasibility success are recommended by the CONSORT statement extension for feasibility trials (Eldridge et al., 2010). No other study investigating the feasibility of wearable technology was identified which had pre-defined criteria for success, therefore criteria for this study were based on the results of previous studies and the recommended data needed for analysis of physical activity. A wear time of 10 hours per day and at least 3 days of data will be considered as the criteria for feasibility success.

7 Population

The study participants will be patients admitted to UHW critical care unit. It is a 33 bedded mixed unit, providing tertiary care for patients from across South and West Wales. Nursing care is provided 1:1 for level 3 care and 1:2 for level 2 care. Patients present with a wide range of medical conditions including post-surgery, polytrauma, respiratory failure and neurological injury. The severity of illness will be variable, but patients admitted to critical care will require support for at least one organ. The majority of patients are likely to be sedated and mechanically ventilated on admission to the unit or shortly afterwards. Patients who do not require mechanical ventilation may require non-invasive ventilation or support for another organ. All patients are screened by physiotherapists at admission and therapy is provided by a team of physiotherapists as part of routine care.

Approximately 125 patients are admitted to this critical care unit each month. It is estimated that approximately 70% of these patients will meet the exclusion criteria. A target sample size of 15 is deemed to be achievable and adequate to evaluate feasibility for this study with this population.

7.1 Inclusion Criteria

1. Age >18
2. 'At risk' of physical morbidity as determined by NICE CG83 guidelines (Appendix C)
3. Advice from consultee for participation and patient re-consent if appropriate for continuing participation

7.2 Exclusion Criteria

1. Age <18
2. Expected to die during admission
3. Failure to obtain consent or advice,
4. Pre-existing neuromuscular disease
5. Unable to wear activPAL™
6. Open abdomen
7. Active neurological event requiring intervention (e.g. EVD, ICP bolt)
8. Acute spinal cord injury
9. Lower extremity fractures
10. Bedbound prior to admission

The exclusion criteria (with the exception of age, pre-existing neuromuscular disease and unable to wear activPAL™) are the same criteria used by the critical care physiotherapy team to decide if a patient is or is not appropriate for rehabilitation input.

8 Study Procedures

8.1 Recruitment

Participants will be recruited from patients within the critical care unit at UHW. Screening of potential participants will be completed through routine daily reviews of patients admitted to the unit. As far as is possible this will occur in order of admission time. Every new patient admitted to the critical care unit will be screened by the principal investigator or member of the critical care research team, all of whom will be part of the direct clinical care team and as such confidentiality will be maintained in accordance with practice. Reviewing identifiable personal information will be required to identify potential participants to establish if they meet the inclusion criteria. This will be achieved through the review of patient's medical notes and their clinical presentation and will include a short assessment using the National Institute for Health and Care Excellence CG83 guidance short clinical assessment tool. This assessment is routine practice within this critical care unit. See Appendix C for details.

GIG
CYMRU
NHS
WALES

Bwrdd Iechyd Prifysgol
Caerdydd a'r Fro
Cardiff and Vale
University Health Board

Ysbyty Athrofaol
Cymru
University Hospital
of Wales

GREAT ORMOND STREET
INSTITUTE OF CHILD HEALTH

Potential participants who satisfy the inclusion and exclusion criteria will be recruited into the study. See section 8.2 for consent.

8.2 Informed Consent

Due to the nature of this study, the wearable device needs to be fitted within the first 24 hours following admission to critical care. This allows the feasibility of using the device to be evaluated at all stages of a patient's admission within critical care. It is likely that the patients will have undergone intubation and initiation of mechanical ventilation during this time. These patients will be sedated as part of their medical management and as such will not be able to provide consent prior to inclusion. It may not be appropriate to approach the relatives before the first measurement is taken so consent will be waived until discussed with an appropriate consultee. A consultee will be approached as soon as is appropriate, which will generally be within 48 hours after admission. A consultee will be identified after discussion with the participant's family and friends and will be approached by either the principal investigator or a member of the Critical Care research team. This will not be the first contact the consultee has with a member of the healthcare team. They will be able to advise on the presumed thoughts and wishes of the participant. Consultees will be provided with an information sheet and after an appropriate time will be asked to sign a consultee declaration form. If the consultee does not wish for the patient to be included in the study, any data previously collected will be destroyed.

Once the participant has regained capacity and is able to provide their consent they will be provided with a patient information sheet by the principal investigator or member of the critical care research team. The participant will be allowed adequate time (at least 24 hours) for consideration prior to signing a participant re-consent form. The PI or member of the critical care research team must record when the patient information sheet (PIS) has been given to the patient. If the amount of time between the PIS being given and the date of consent is less than 24 hours, the PI needs to explain the rationale for this.

If new safety information results in significant changes in the risk/benefit assessment, the consent form will be reviewed and updated if necessary and subjects will be re-consented as appropriate. Due to the nature of critical illness, it may be some time between inclusion and re-consenting. The re-consent process is to ensure that the participant is willing for the data previously collected to be used as part of the study, and that they are happy for data collection to continue. If they do not consent they will be asked if data previously collected can be used for the study or if they wish for it to be destroyed.

The PI and members of the critical care research team have all received Good Clinical Practice training. The PI has also received valid informed consent training and mental capacity act training. Members of the research team have received additional consent training and are experienced in taking consent from patients and consultees in the critical care environment.

8.3 Screening and Eligibility Assessment

Demographic information of age, medical history and diagnosis will be screened for to check against the inclusion and exclusion criteria for eligibility.

A patient's risk of developing physical morbidity will be assessed using the National Institute for Health and Care Excellence CG83 guidance short clinical assessment tool (see appendix C). If four or more of the criteria are met the patient will be determined as at risk of developing physical morbidity and will be eligible for inclusion in the study.

Participant's baseline mobility status will be checked to ensure exclusion criteria item 10 is not applicable.

No additional tests or examinations are required.

8.4 Baseline Assessments

For all recruited patients, demographic information will be recorded at critical care admission. This information will be gender, date of birth, diagnosis, ventilation status and severity of illness using the acute physiology and chronic health evaluation 2 (APACHE II) score. Length of mechanical ventilation and critical care stay will be recorded on discharge from the unit.

8.5 Data Collection

Data collection will not start until approval is received from the REC and R&D.

Participants will not be expected to do anything different to normal as part of the study except wear an activPAL™ device on their thigh for the duration of their critical care admission. This will be applied to the patient by the PI, clinical supervisor or member of the critical care research team, all of whom will be part of the direct clinical team. This will take place on the critical care unit and will not require the patient to be moved. The device will be placed on the participant's right thigh unless this is prohibited by lines, wounds or dressings when it will be placed on the left thigh. The device will not be placed on areas of skin that appear marked or broken. Fitting the device does not require any specialist training and all instructions from the manufacturer will be followed. The device will be covered in a waterproof dressing so that it will not need to be removed during routine personal care. All devices will be fully charged and calibrated prior to application.

In addition, once the device is fitted, the critical care the nursing staff looking after the participant will fill out a simple record sheet each hour during the day shift to document the participant's activity. The activity observation data collection sheet will be based on one previously used in a UK research study (Connolly et al., 2017). This data is routinely collected by physiotherapists on the unit at each therapist-patient contact but is not routinely collected hourly by the nursing staff. Recording observed activity will be performed to further explore the feasibility of the data collected from the wearable device. Once completed at the end of each shift the record sheets will be stored in the site file and transferred onto an electronic spreadsheet at the earliest opportunity. The site file will be kept in a locked office which is only accessible by the research team

A priori criteria for feasibility success are recommended by the CONSORT statement extension for feasibility trials (Eldridge et al., 2010). No other study investigating the feasibility of wearable technology was identified which had pre-defined criteria for success, therefore criteria for this study were based on the results of previous studies and the recommended data needed for analysis of physical activity. A wear time of 10 hours per day and at least 3 days of data will be considered as the criteria for feasibility success.

8.5.1 Wearable device

The activPAL™ (PAL Technologies Limited) is the chosen wearable device for collecting activity data. The device is CE marked and will be used for its intended purpose. The activPAL™ classifies an individual's activity into periods spent sitting, standing and walking. This wearable accelerometer device sticks to the participant's thigh, which may be more appropriate than the more traditional wrist watch design as critical care patients often have lines and cannulae inserted into their wrist/forearm which may preclude wearing a watch device.

No intervention is being investigated as this is an observational study. Consequently, there are unlikely to be any adverse or detrimental effects to the participant. However, it is possible the participant may experience some mild discomfort from the device on the skin. This will be monitored by the healthcare team. The device will not be placed on areas of skin that appear marked or broken. If there are any concerns the advice of tissue viability nurses will be sought. If the participant experiences discomfort and asks for the device to be removed the device will be taken off. The participant will be asked whether the data collected from the device can be used for the study or if they wish for the data to not be included in the research.

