9.1 Statistical methods / plan of analysis

This study aims to evaluate the feasibility of using a wearable device and inform the design of a future trial, rather than to detect statistically significant differences; therefore, a formal sample size calculation has not been completed (Arain et al., 2010). The sample size needs to be suitable to allow evaluation of the feasibility parameters taking into account the likely recruitment rate (Eldridge et al., 2016). Based on previous data, it is estimated that 375 of patients will be admitted to the unit within a 12 week period and 70% are likely to meet the exclusion criteria, leaving approximately 112 eligible participants. With a minimum of five devices available and an average length of admission for 'at risk' patients of 14 days, a sample size of 15 is deemed to be achievable and adequate to evaluate feasibility.

Descriptive data (see section 5 primary outcome measures) from the activPAL™ will be summarised using tables and presented using graphs. As there is no hypothesis testing, no statistical tests will be performed. The feasibility outcomes will be compared against the a priori criteria for success.

Comparisons will be made between the activity levels detected by the wearable device, and staff-reported activity using percentage agreement. Descriptive data for the secondary outcome measures (see section 5) will be summarised using tables.

Due to the small size of the study there is no planned interim analysis.

10 Data Management

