16.4 Appendix D: Activity observation recording sheet

ACTIVE [IRAS ID 238464]

Study ID:

Ventilation status:

Date:	0700-	0800-	0900-	1000-	1100-	1200-	1300-	1400-	1500-	1600-	1700-	1800-
Activity / Time	0800	0900	1000	1100	1200	1300	1400	1500	1600	1700	1800	1900
Routine turn/personal care												
0 Nothing/lying in bed												
0a Purposeful upper limb movement												
1 Sitting in bed/exercises in bed												
2 Passively moved to chair												
3 Sitting over the edge of the bed												
3a Seated position in chair												
4 Standing												
5 Transferring from bed ↔ chair												
6 Marching on the spot												
7 Walking with assistance of 2												
8 Walking with assistance of 1												
9 Walking independently with an aid												
10 Walking independently with no aid												

Please note the time and any reasons for occasions when the device had to be removed e.g. for scan, to change dressings, to charge device.

GIG
CYMRU
NHS
WALES

Bwrdd Iechyd Prifysgol
Caerdydd a'r Fro
Cardiff and Vale
University Health Board

Ysbyty Athrofaol
Cymru
University Hospital
of Wales

GREAT ORMOND STREET
INSTITUTE OF CHILD HEALTH

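### A capture percentage pooled over all postures cannot show whether the device detects upright activity, because seated entries may agree by default

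*Combined protocol and SAP*

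**What the plan says.** - **Device.** Section 8.5.1 says that the device classifies "activity into periods spent sitting, standing and walking". No lying class is named. Section 8.5 describes one sensor on one thigh: "The device will be placed on the participant's right thigh unless this is prohibited by lines, wounds or dressings". Section 10.3 names the analysis software without listing its output classes.
- **Reason for the choice.** The end of section 4.1 contrasts the device with an earlier armband that missed position changes: "An accelerometer, which can detect changes in position, may be a more appropriate method of monitoring activity on critical care".
- **Outcome.** Section 5 lists "Percentage of activities observed by nursing staff recorded by activPAL™ device" among the primary feasibility outcomes. Section 9.1 compares the device with "staff-reported activity using percentage agreement". Neither section says which sheet rows count as activities, which device class each row should match, what counts as a match within an hour, or whether results are split by posture.
- **Sheet.** Appendix D has 12 hourly columns from 0700 to 1900. Its rows cover routine turns and personal care, lying (0), upper-limb movement (0a), four seated rows (1, 2, 3 and "3a Seated position in chair") and seven upright rows (4 to 10).
- **Success criteria.** Sections 6.1 and 8.5 set criteria for daily wear time and days of data. The capture percentage has no threshold.

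**The concern.** Wear time, days worn and adverse events show whether the device can be kept on a patient safely. Capture is the only primary outcome that bears on whether the device measures what the patient does.

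On the three classes described, a patient who is not upright has one plausible class, sitting. If lying is logged there, a nurse's entry in a seated row agrees with the device whether the patient has just been moved or has not moved all day. Such agreement says nothing about detection. In a population chosen because it is likely to be minimally active, upright entries may be few, and non-upright entries could then dominate a pooled percentage. A reader could take a high figure as evidence that the device works when no stand, transfer or walk was picked up. The stated reason for preferring an accelerometer, detection of position change, would go partly untested.

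**Working it through.** The plan gives no expected value, threshold or precision for capture, so there is no figure to reproduce. The check asks what the pooled percentage would be for a device that detects no standing or walking and always reports sitting.

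**Inputs**
- Device classes: sitting, standing, walking (section 8.5.1).
- Sheet rows: lying 0; seated 1, 2, 3, 3a; upright 4 to 10 (Appendix D).
- *L*, the share of entries that are lying, and *U*, the share that are upright. The documents give neither; section 4.1 says only that overall activity is very low. Both are assumptions.
- The remaining share, 1 − *L* − *U*, is treated as seated. Row 0a and routine turns are set to zero at first.

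**Four scoring rules the plan would allow**
- A. All rows count; lying and seated both match: capture = 1 − *U*.
- B. Row 0 is left out: capture = (1 − *L* − *U*) / (1 − *L*).
- C. All rows count; lying is a mismatch because it has no class: capture = 1 − *L* − *U*.
- D. Upright rows only: capture = 0.

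**Results at *U* = 5%**

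| *L* | A | B | C | D |
|---|---|---|---|---|
| 30% | 95% | 0.65/0.70 = 93% | 65% | 0% |
| 50% | 95% | 0.45/0.50 = 90% | 45% | 0% |
| 70% | 95% | 0.25/0.30 = 83% | 25% | 0% |
| 90% | 95% | 0.05/0.10 = 50% | 5% | 0% |

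**Varying *U***
- Rule A gives 98% at *U* = 2% and 92% at *U* = 8%.
- At *L* = 90% and *U* = 8%, rule B gives 0.02/0.10 = 20% and rule C gives 2%.
- On a 12-hour sheet with one entry per hour and *k* upright hours, rule A gives (12 − *k*)/12: 91.7% for one upright hour, 83.3% for two, 75.0% for three and 50.0% for six.

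**How little upright detection moves the figure.** If the device detects a fraction *u* of upright entries, rule A gives (1 − *U*) + *U* × *u*. At *U* = 8%, going from no detection to perfect detection moves capture only from 92% to 100%. At *U* = 2% it moves from 98% to 100%.

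**Rows left out.** If row 0a and routine turns make up a share *z* of entries and count as misses, rule A falls to 1 − *U* − *z*. The documents give no basis for *z*.

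**What the classes can and cannot check.** Sitting-to-upright change can be checked, because the sheet has rows 4 to 10 and the device has standing and walking classes. Lying versus sitting in bed, and bed versus chair, cannot be checked on the described classes. Section 5 nevertheless lists chair time and bed time as separate secondary outcomes.

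**The case against.** The strongest reply is that the plan states no scoring rule, so it cannot be faulted for one that inflates agreement. The same blind device scores anywhere from 2% to 98% under rules A to C. This stands against any claim that the figure will be high. It does not rescue the pooled figure: one that moves that far for a device with no upright detection does not measure upright detection.

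Second, the missing lying class rests on one descriptive sentence. The software may output more classes, or may leave lying unclassified, and agreement by default would then disappear. This stands, and the conclusion is conditional on it.

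Third, a reader might infer that the study cannot test position-change detection at all. The documents do not support that, because rows 4 to 10 allow sitting-to-upright change to be tested once they are reported separately.

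Fourth, it is tempting to assume that seated rows form most activity entries and to quote a high floor for capture. No source gives that share. Minimal activity points as readily to many lying entries, and row 0a, routine turns, bed exercises (within row 1) and passive moves (row 2) are not plainly matched by a sitting output.

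Finally, section 8.5 presents the nurse observations as further exploration of feasibility, and capture carries no threshold. A reader might infer that the feasibility decision is compromised; the stated criteria do not use this outcome.

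**Conclusion.** The point holds in a limited form. As described, the device has no lying class, and sections 5 and 9.1 pool lying, seated and upright rows into one agreement figure. If lying is logged as sitting, seated entries can agree by default. The pooled percentage then reflects the activity mix and the scoring rule, and can be high with no standing or walking detected: 92% to 98% if all rows count and 2% to 8% of entries are upright.

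Those shares, and the logging of lying as sitting, are assumptions; under other rules and mixes the figure can be far lower. What follows in either case is that the pooled figure does not show whether upright activity is detected. On the described classes, it also cannot verify lying versus sitting or bed versus chair. The consequence is for the interpretation of one primary outcome. The success criteria on wear time and days are untouched.

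**What to change.** In sections 5 and 9.1, replace the single pooled percentage with capture by posture group:

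1. **Lead with upright entries.** Report the share of nurse-recorded entries in rows 4 to 10 for which the device shows standing or walking in that hour, with the number of entries. A device that detects neither then scores 0%, whatever the mix.
2. **Report seated rows 1, 2, 3 and 3a separately.** If the device output cannot separate lying from sitting, label them *not assessable* and leave them out of the percentage.
3. **Report row 0a and routine turns separately**, because no device class is described for them.
4. **Do not require a change of position in each hour** before a seated entry counts. A patient who sits for several hours would be scored as missed although the device was right.

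The cost is wording and a short recoding of data already being collected. The drawback is a smaller denominator. With 15 participants, the 14-day average stay in section 9.1, 12 columns a day and one entry per hour (assumed, with complete sheets), there would be 15 × 14 × 12 = 2,520 entries. Upright shares of 2%, 5% and 8% leave about 50, 126 and 202. These would be clustered within participants, so the leading percentage will be less precise than the pooled one and should be shown with its count.
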